1.5. Randomization and Blinding

A centralized randomization strategy will be implemented in this study. Subjects will be randomly assigned in a 1:1 ratio to 1 of 2 treatment groups based on a computer-generated subject-randomization schedule prepared by or under the supervision of the sponsor prior to initiation of the study. The randomization will be stratified by tumor type (Advanced Pancreatic Cancer [APC] or non-APC) such that up to approximately 25% of the subjects randomly assigned are those with APC. Using the randomization schedule, the IWRS will assign treatment. The IWRS will also provide the number of the study drug bottle to be dispensed for each randomly assigned subject on Day 1 and at each visit (except Day 180/End-of-Treatment) during the double-blind treatment period. The requestor must use his or her own user identification (ID) and personal identification number (PIN) when contacting the IWRS and will then be asked to provide relevant subject details to uniquely identify the subject. Based on these randomization codes, the study drug will be packaged and labeled in a manner that maintains the double-blinded nature of this study.

The investigator will not be provided with randomization codes. The codes will be maintained within the IWRS, which has the functionality to allow the investigator to break the blind for an individual subject.

Data that may potentially unblind the treatment assignment (ie, events that contribute to the primary and secondary outcome or treatment allocation) will be handled with special care to ensure that the integrity of the blind is maintained and the potential for bias is minimized. This can include making special provisions, such as segregating the data in question from view by the investigators, clinical team, or others as appropriate until the time of database lock and unblinding.

Pancreatic cancer subjects are at a higher risk to develop VTE (VTE Khorana risk score ≥ 2). These subjects are also more likely to discontinue early from the study. Therefore, higher than planned (25%) number of pancreatic subjects were allowed for enrollment into this study.

2. GENERAL ANALYSIS DEFINITIONS

2.1. Visit Windows

Data collected in the study from randomization through End-of-Double-Blind (EODB) will be re-assigned to visit windows based on the actual date of assessment (only for the ECOG performance status evaluation, laboratory and vital signs data).

The reference day is Study Day1 which will correspond to the randomization day. The relative day will be determined relative to Study Day 1.

The visit windows are based on the scheduled clinic visits (see Time & Events Schedule in protocol) and are defined below:

Period	Visit Window	Time Intervals ^a for Visit Window	Target Day ^a for Visit Window
Screening/Randomization	Baseline	≤1	1
Double-Blind Period	Week 8	>1 to 84	56
	Week 16	85 to 146	112
	Day 180/EODB ^b	≥147	180

^a Based on actual study day of assessment; b = End of Double-Blind Period. No lab or vital signs data were collected at the Day 210 Follow-Up/End-of-Study visit

If more than one assessment falls in the same visit window, the one closest to the target date will be used in summary tables. In case of a tie (2 or more assessment which are equidistant), the latter assessment will be used.

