2.5. Definition of Study Dates and Observation Period End Dates

The study dates and period end dates will be used to define the time period for data included in the analysis of efficacy and safety endpoints for the different observation periods (defined in Section 2.6).

Study Day 1 date: the date of randomization of the subject.

End-of-Study (EOS): the date of the last study-related procedure for the subject (EOS is defined as last assessment day during the study, including the Day 210/Post-Treatment Follow Up visit) and is defined as the minimum (last assessment day during the study, death date).

Double-Blind period start date will be the date of randomization.

Double-Blind period end date will be defined as the completion/early withdrawal date (date of completion or early withdrawal [any reason including death] from the double-blind period).

Up-to-Day 180 observation period end date will be defined as follows;

- Day 180/EODB completion date (for subjects who completed the double-blind period) or
- Death date (subjects who died during the double-blind period [DB reason=death] or during any time from randomization through Day 180 [died post withdrawal from DB but before Day 180/EODB visit] or
- Maximum (double-blind withdrawal date, randomization date + 180 days) for subjects who withdrew early from the double-blind period [any reason other than death] and had not died during the time from randomization through Day 180

First dose date: the date on which the first dose of study drug is taken by the subject. If missing or partial for a subject who takes study drug, the first dose date is set to the randomization date.

Last dose date: the date on which the last dose of study drug is taken by the subject (dose end date). If the dose end date is missing or partial for a subject who takes study drug, the last dose date is set as follows

- Maximum (Minimum (discontinuation date in the double-blind period [including death date during double-blind period], last visit date when drug is dispensed + number of pills dispensed - number of pills returned at following visit), imputed partial last dose date, exposure start date of last record))
 - Imputation rule for partial dates: If only the day is missing, then day imputed to the last day of that month. If day and month are missing, the date will be imputed to the start date if year is the same, else imputed to January 1st.

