6.3. Clinical Laboratory Tests

Descriptive statistics for each clinical laboratory analyte (collected at baseline and at Week 8, Week 16, and EODB) will be provided. Changes from baseline at each post-baseline visit will be calculated by treatment group and will be based on the safety population in the ‘Up-to-Day 180’ observation period. The number of shifts from baseline in the categories of test results (low, normal, high) will be summarized by treatment group. A clinical laboratory test value is considered abnormal if it is outside the reference range (provided by the laboratory). Incidences of abnormal laboratory values will be summarized by treatment group based on subjects who have non-missing baseline and non-missing post-baseline values.

All laboratory test summaries will be based on the safety population (data from first dose through Day 180). Laboratory data from the central lab Covance will only be included in the summaries.

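### Read literally, the closest-to-target window rule also governs the incidence of abnormal laboratory values, which can then be understated when a window holds more than one value

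*SAP*

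**What the plan says.** SAP section 2.1 sets three post-baseline windows: Week 8 (after Day 1 to Day 84, target Day 56), Week 16 (Days 85-146, target Day 112) and Day 180/EODB (Day 147 onward, target Day 180). Data "will be re-assigned to visit windows based on the actual date of assessment", and this holds "only for the ECOG performance status evaluation, laboratory and vital signs data". The selection rule is: "If more than one assessment falls in the same visit window, the one closest to the target date will be used in summary tables". A tie goes to the later value. No type of summary table is exempted.

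Section 6.3 says laboratory analytes are "collected at baseline and at Week 8, Week 16, and EODB". It plans descriptive statistics and changes from baseline by visit, shifts between low, normal and high, and an incidence of abnormal values. On the incidence it says: "Incidences of abnormal laboratory values will be summarized by treatment group based on subjects who have non-missing baseline and non-missing post-baseline values". This fixes which subjects are counted. It does not fix which of a subject's post-baseline values count. The same section restricts all laboratory summaries to the safety population, to data from first dose through Day 180, and to the central laboratory.

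**The concern.** One value per window, closest to target, is a sound choice for by-visit means and changes. An incidence asks a different question: was the subject abnormal at any time after baseline? For that question every value matters. Leaving one out can lower the count or leave it unchanged, but cannot raise it. The denominator does not move, because a subject with any post-baseline value in a window keeps at least one.

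The windows are contiguous and wide, and assignment follows the actual date. A sample taken at early withdrawal therefore competes with the scheduled Week 8 or Week 16 sample rather than standing as an EODB value. A central recheck between visits would compete in the same way. These are plausibly the samples in which an abnormality appears, although the SAP has no data on that. At stake is the completeness of a descriptive safety table.

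**Working it through.** The SAP states no figure for this point, so there is none to reproduce. The check applies the rule in section 2.1 to hypothetical samples.

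**Inputs from the SAP**
- Window limits, target days, closest-to-target selection and tie rule: section 2.1.
- Planned dropout of 20%: section 1.4.
- Timing of an EODB sample, section 2.5: "Double-Blind period end date will be defined as the completion/early withdrawal date". A sample taken at early withdrawal can thus fall on any day, and section 2.1 places it in the window of that day.

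**Assumptions, not in the SAP**
- Scheduled samples fall exactly on Days 56 and 112.
- One central-laboratory sample is taken on the day of each withdrawal.
- Withdrawal days are spread evenly over Days 2-179, which is 178 days.
- q, the probability that the dropped sample is abnormal and no retained sample is, ranges from 5% to 50%.

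**Step 1: windows.** The limits are the midpoints between targets: (56 + 112)/2 = 84 and (112 + 180)/2 = 146. Week 8 spans 84 − 2 + 1 = 83 days and Week 16 spans 146 − 85 + 1 = 62 days.

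**Step 2: which withdrawal samples are dropped.**

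| Withdrawal day | Other sample in the window | Withdrawal sample |
|---|---|---|
| 2-56 | none | kept |
| 57-84 | Day 56, distance 0 | dropped |
| 85-112 | none | kept |
| 113-146 | Day 112, distance 0 | dropped |
| 147-179 | none | kept |

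Dropped days: (84 − 57 + 1) + (146 − 113 + 1) = 28 + 34 = 62. Share: 62/178 = 34.8%.

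Two examples: with samples on Days 56 and 75, the distances are 0 and 19, so Day 75 is dropped. With an unscheduled central sample on Day 20 and a scheduled one on Day 56, the distances are 36 and 0, so Day 20 is dropped.

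Off-target visits change the result. With samples on Days 45 and 60 the distances are 11 and 4, so the Day 60 withdrawal sample is kept.

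**Step 3: subjects who lose a sample.** 0.20 × 0.348 = 0.070, or about 7%.

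**Step 4: effect on the incidence.** Maximum understatement = dropout × share dropped × q.

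| q (assumed) | 20% dropout | 40% dropout (assumed) |
|---|---|---|
| 5% | 0.35 points | 0.70 points |
| 10% | 0.70 points | 1.4 points |
| 20% | 1.4 points | 2.8 points |
| 50% | 3.5 points | 7.0 points |

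The 40% column is an illustration only. It is shown because section 1.2 reports more discontinuation than anticipated without giving a rate. Unscheduled central samples would add to these figures, but the SAP gives no basis for a number.

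**The case against.** The strongest reply is that section 2.1 decides which value represents a visit, and the incidence sentence in section 6.3 names no visit. The sponsor may never have meant the window rule to reach that table. Section 1 also places programming instructions in a separate Data Presentation Specifications document, which could settle the point. This stands in part: it is not established that the incidence will be computed from windowed values. It does not repair the text, because section 2.1 states its rule for summary tables without exception and section 6.3 supplies no other.

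A second reply is that the samples at issue are partly hypothetical. Section 6.3 lists only scheduled collections, and the SAP describes no unscheduled central tests. Stopping study drug does not end follow-up (sections 1.2.1 and 4.6), and withdrawal from the double-blind period includes death (section 2.5). This also stands, and it makes 7% an upper figure under the stated assumptions.

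A third reply is that serious signals have other routes. Adverse events are summarized by onset date (section 6.2), the events of special interest include raised liver tests (section 6.2.4), and a hemoglobin fall with overt bleeding enters the adjudicated bleeding classification (section 6.1.1). These routes limit the consequence but do not correct the laboratory table.

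A reader might infer more than the SAP supports:
- That withdrawal and unscheduled results are discarded in general. The rule acts only when a window holds two or more values, and a value nearer the target is the one kept.
- That about 7% of subjects have a missed abnormality. That figure counts samples not selected.
- That the window rule removes local-laboratory results. Those are excluded by the central-laboratory sentence in section 6.3.
- That the comparison between arms is biased. This would need different withdrawal or testing patterns by arm, and the SAP gives none.

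**Conclusion.** The point holds as a defect of wording with a possible, limited effect. Taken literally, the SAP lets an abnormal central-laboratory value go unused in the incidence table because another value in the same wide window is closer to target. The incidence can then only be lowered.

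Under on-time visits, even withdrawal times, a central sample at every withdrawal and 20% dropout, the loss is about 0.35 to 3.5 percentage points for q between 5% and 50%. That an understatement will occur is not shown.

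By-visit means, changes and by-visit shifts are properly served by the rule. Efficacy, bleeding and adverse event analyses are outside it, because section 2.1 limits the windows to ECOG, laboratory and vital signs data. The correction is worth making because the output is a safety table and the change is nearly free.

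**What to change.** In section 2.1, state that the closest-to-target rule applies only to by-visit summaries: means, changes from baseline and by-visit shifts. In section 6.3, state that the incidence of abnormal values uses all post-baseline central-laboratory results through Day 180, including unscheduled and early-withdrawal samples. A table of shifts from baseline to the worst post-baseline value is an optional addition.

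The cost is two sentences and one more derived flag, with no new data. The reported incidences may be slightly higher than under the windowed rule.

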2.2. Baseline

Baseline value is defined as the last observation prior to and including Day 1.

2.3. Pooling Algorithm for Analysis Centers

No pooling of centers (with varying number of randomized subjects) will be done.

2.4. Analysis Populations

2.4.1. Intent-to-Treat (ITT) Population

This analysis population consists of all randomized subjects.

2.4.2. Per-Protocol (PP) Population

This population is a subset of the ITT population. Subjects with predefined major protocol deviations will be excluded from the ITT population.

The predefined protocol deviations (based on major deviations) employed to define the PP population are:

- Randomized without informed consent (entered study but inclusion criterion #12 not met)
- Received wrong treatment (deviation recorded to be received wrong treatment or incorrect dose)
- Randomized but not treated
- Randomized but did not satisfy the key study entry criteria (inclusion criteria not met/exclusion criteria met)
 - Inclusion Criteria
 - #1 Ambulatory men and women ≥ 18 years of age
 - #4 Subject must have a Khorana thromboembolic risk score ≥ 2
 - Exclusion Criteria
 - #1 Subject has diagnosis of primary brain tumors
 - #2 Subject has known history of brain metastases
 - #3 Subject has bleeding diathesis, hemorrhagic lesions, active bleeding and other conditions with a high risk for bleeding
 - #4 Subject has hematologic malignancies with the exception of lymphoma
 - #8 Subject has evidence of VTE on screening Compression Ultrasound or incidental VTE identified on spiral computed tomography scans ordered primarily for staging or restaging of malignancy ≤ 30 days prior to randomization

All protocol deviations, including the deviations listed above will be examined and reviewed from a medical perspective prior to End-of-Study/database lock in a blinded fashion and subjects will be flagged accordingly in the final analysis database.

2.4.3. Safety Population:

This population is a subset of the ITT population, consisting of all randomized subjects who receive at least one dose of study drug.

2.5. Definition of Study Dates and Observation Period End Dates

The study dates and period end dates will be used to define the time period for data included in the analysis of efficacy and safety endpoints for the different observation periods (defined in Section 2.6).

Study Day 1 date: the date of randomization of the subject.

End-of-Study (EOS): the date of the last study-related procedure for the subject (EOS is defined as last assessment day during the study, including the Day 210/Post-Treatment Follow Up visit) and is defined as the minimum (last assessment day during the study, death date).

Double-Blind period start date will be the date of randomization.

Double-Blind period end date will be defined as the completion/early withdrawal date (date of completion or early withdrawal [any reason including death] from the double-blind period).

Up-to-Day 180 observation period end date will be defined as follows;

- Day 180/EODB completion date (for subjects who completed the double-blind period) or
- Death date (subjects who died during the double-blind period [DB reason=death] or during any time from randomization through Day 180 [died post withdrawal from DB but before Day 180/EODB visit] or
- Maximum (double-blind withdrawal date, randomization date + 180 days) for subjects who withdrew early from the double-blind period [any reason other than death] and had not died during the time from randomization through Day 180

First dose date: the date on which the first dose of study drug is taken by the subject. If missing or partial for a subject who takes study drug, the first dose date is set to the randomization date.

Last dose date: the date on which the last dose of study drug is taken by the subject (dose end date). If the dose end date is missing or partial for a subject who takes study drug, the last dose date is set as follows

- Maximum (Minimum (discontinuation date in the double-blind period [including death date during double-blind period], last visit date when drug is dispensed + number of pills dispensed - number of pills returned at following visit), imputed partial last dose date, exposure start date of last record))
 - Imputation rule for partial dates: If only the day is missing, then day imputed to the last day of that month. If day and month are missing, the date will be imputed to the start date if year is the same, else imputed to January 1st.

The last dose date will not be later than the double-blind period end date. The last dose date will not be before the first dose date and if a subject has not taken any study drug, the last study drug date will be set to missing.

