1.2.1. Study Drug Discontinuation and Early Withdrawal from Double-Blind Period

As per the protocol (Section 10.2.2), if a subject permanently discontinued study drug before the Day 180 visit/End of double-blind (EODB) period, this would not result in automatic permanent withdrawal of the subject from the study. Subjects are encouraged to make every effort to continue participation in the study and complete the schedule subsequent study visits until the planned end of their study double-blind duration (Day 180/EODB). All outcomes/events data (VTE, vital status (alive/dead), MI, stroke, and other thrombosis events) and safety data (including bleeding events) are collected. If a subject permanently discontinued study drug prior to Day 180 but continued in the study and completed all study visits up to Day 180, then this subject is considered as having ‘completed the double-blind period’ (that is, participated in the study up to the Day 180 visit).

All subjects including those who discontinued prior to Day 180 visit are contacted by telephone for a Day 210/EOS follow-up assessment. Any outcome/event data (including vital status) reported during this telephone visit is collected at this Day 210/EOS visit as agreed upon by the subject informed consent. In the event a subject withdrew consent or is lost-to-follow up, the vital status data are obtained through public information (death and other registries) per local guidelines and as allowed by local registration.

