2.6.3. Post-Randomization Observation Period

This observation period includes all data from randomization to Day 210/EOS.

Specifically, this observation period will include all events that have occurred after randomization through Day 210/EOS inclusive of all events after completion of double-blind period/Day 180 through Day 210 as well as all events that occurred after subject had withdrew early from the double-blind period through Day 210.

Event: All efficacy events (with respect to deaths, *VTE-related deaths are counted as events for primary efficacy composite endpoint*) that occurred from the date of randomization up to the Day 210/End-of-Study [EOS] (defined in Section 2.5) will be included in the analysis of the Post-Randomization observation period.

- Event time - The time to event is defined as the time from randomization to the time of the first event during this observation period.

Censoring: Subjects who do not experience an event during this observation period will be censored.

Subjects who died during this observation period will be censored as of their death date for endpoint analysis not related to death.

- Censoring time - The time to censoring will be time from randomization to the minimum of (last contact date [up to and including the Day 210 = EOS date defined in Section 2.5], death date [non VTE-related deaths]).

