2.6.4. Post-First Dose Observation Period

This observation period includes all data from the first dose of study drug to Day 210/EOS.

Specifically, this observation period will include all events that have occurred after first dose through Day 210 inclusive of all events after double-blind period completion/Day 180 through Day 210 as well as all events that occurred after subject had withdrew early from the double-blind period through Day 210.

All randomized subjects will be included and the imputation rule for event times for randomized subjects but never dosed described in Section 2.6.2 will also be applied for the analysis of data for this observation period. All events that occur prior to the End-of-Study date will be included in the post-first dose observation period.

Event: All efficacy events (with respect to deaths, *VTE-related deaths are counted as events for primary efficacy composite endpoint*) that occurred from the date of first dose up to the Day 210/End-of-Study[EOS] (Section 2.5) will be included in the analysis of the Post-First Dose observation period.

- Event time - The time to event is defined as the time from first dose date to the time of the first event during this observation period.
 - For randomized subjects but never dosed: The time to event will be defined as the time from randomization to the time of the event during the time in study. This imputation rule will be applied only for the ITT population.

Censoring: Subjects who do not experience an event during this observation period will be censored.

Subjects who died during this observation period will be censored as of their death date for endpoint analysis not related to death.

- Censoring time - The time to censoring is defined as the time from first dose date to the minimum (earliest) of (last contact date [up to and including Day 210 visit date = EOS date defined in Section 2.5], death date [non VTE-related deaths])
 - For randomized subjects but never dosed: The time to censoring will be defined as the time from randomization to the minimum of (last contact date [up to and including Day 210=EOS date, death date [non VTE-related deaths]]).

Examples are illustrated in Figures in the Appendix.

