 - a. If subject experiences an efficacy composite endpoint event (primary or secondary, including VTE-related deaths) after withdrawing from the study and the time to the occurrence of the event is prior to Day 180, then this event and corresponding time to the occurrence of the event will be included in the analysis of primary efficacy composite endpoint. If subject dies (all causes other than VTE-related) after withdrawing from the study and reported on Day 210 but event time is prior to Day 180, then this event and corresponding time to death will be included in the all-cause mortality endpoint analysis
 - b. If a subject does not experience any efficacy composite endpoint event (primary or secondary) in the study, then this subject will be censored. The time to censoring is defined as the time from randomization to the minimum of (last day of their complete assessment for study outcomes during the double-blind period/Day 180 [double-blind withdrawal date for those who withdrew], or death date [censored at death date for analysis not related to the specific death endpoint]).

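### As written, the SAP's End-of-Study date shuts some VTE-related deaths out of the two supportive windows meant to run through Day 210

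*SAP*

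**What the plan says.** Section 2.5 describes EOS as "the date of the last study-related procedure for the subject", including the Day 210 follow-up visit, and then gives the formula: it "is defined as the minimum (last assessment day during the study, death date").

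Sections 2.6.3 (Post-Randomization) and 2.6.4 (Post-First Dose) take events up to Day 210/EOS and cite Section 2.5 for that date. Their censoring rules go further and equate Day 210 with the Section 2.5 EOS date. Yet 2.6.3 also says that its window holds events after Day 180 "as well as all events that occurred after subject had withdrew early from the double-blind period through Day 210", and 2.6.4 has a parallel statement. Section 2.6.4 adds a second inclusion sentence: "All events that occur prior to the End-of-Study date will be included in the post-first dose observation period".

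The primary window is built differently. Its end date in Section 2.5 is "Death date (subjects who died during the double-blind period [DB reason=death] or during any time from randomization through Day 180", and the text expressly covers those who "died post withdrawal from DB but before Day 180/EODB visit". Section 4.6 agrees: an event, VTE-related death included, that occurs "after withdrawing from the study and the time to the occurrence of the event is prior to Day 180" goes into the primary analysis.

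**The concern.** The Post-Randomization window should contain everything in the Up-to-Day 180 window plus what happens up to Day 210. Because EOS is the earlier of two dates, a death can never move it later than the last assessment. A death that no assessment follows is therefore outside a window whose stated purpose is to include it, while the shorter primary window counts it.

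Section 5.2.3 uses these two analyses to test the robustness of the primary conclusion. If the formula is programmed literally, they can lose fatal events that the primary analysis counts, chiefly from subjects who die between visits or after leaving the study. The composite lists only non-fatal PE as a PE event apart from incidental PE, so a fatal PE enters as VTE-related death. If that subject had no earlier qualifying event, the record changes from an event to a censored observation.

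**Working it through.** No figure in the SAP needs reproducing; this is a check of date rules. Days are counted from randomization.

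**Rules**
- L = last assessment day, W = double-blind withdrawal day, D = death day.
- Section 2.5: EOS = min(L, D).
- Section 2.5: Up-to-Day 180 end = completion day for completers; D if death falls by Day 180; otherwise max(W, 180).
- Section 2.6.3, and the event rule of 2.6.4: a death counts if D ≤ EOS.
- The second inclusion sentence of 2.6.4, read literally: a death counts if D < EOS.

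**General result.** D ≤ min(L, D) holds only when D ≤ L. A death is inside the longer windows only if some assessment is dated on or after it. Under the strict sentence in 2.6.4, D < min(L, D) can never hold, so read literally that sentence admits no death at all.

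**Five hypothetical subjects** (illustrations, not trial data)

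| Case | L | D | EOS | Up-to-Day 180 end | In Up-to-Day 180? | In Post-Randomization? |
|---|---|---|---|---|---|---|
| (a) Dies in double-blind period between visits | 56 | 100 | min(56, 100) = 56 | 100 | yes | no |
| (b) Withdraws Day 60, no later contact | 60 | 120 | min(60, 120) = 60 | 120 | yes | no |
| (c) Withdraws Day 60, Day 210 contact made | 210 | 120 | min(210, 120) = 120 | 120 | yes | yes |
| (d) Completes Day 180, no Day 210 contact | 180 | 195 | min(180, 195) = 180 | 180 | no | no |
| (e) Withdraws Day 60, no later contact | 60 | 195 | min(60, 195) = 60 | max(60, 180) = 180 | no | no |

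One death in five is inside the Post-Randomization window. Taking last contact as the last assessment, subject (a) is censored at Day 56 instead of having an event at Day 100, and subject (b) is censored at Day 60 instead of having an event at Day 120.

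- Cases (a) and (b) show the inversion: counted in the shorter window, missing from the longer one.
- Case (c) shows that the formula works when a Day 210 contact follows the death.
- Cases (d) and (e) are not inversions, since the primary window does not count them either. They still conflict with the statement that events through Day 210 are included.

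Case (a) is the plainest route. Ultrasound visits are 8 weeks apart (Section 1.2), and Section 5.7 says that Day 210 vital status was not collected for subjects who died in the double-blind period.

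**With EOS = D when D ≤ 210, and otherwise the last assessment or contact date:** EOS becomes 100, 120, 120, 195 and 195, and all five deaths fall inside the window.

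**The case against.** The best reply is that the intent is plain. Sections 2.6.3 and 2.6.4 say that events through Day 210 are included and that VTE-related deaths count, and they limit the death term in the censoring rule to deaths that are not VTE-related. A sensible programmer would follow this over a general date definition. The minimum in Section 2.5 also makes sense only if an assessment can be dated after death, which suggests that vital-status follow-up was meant to count as one. Section 1.2.1 plans a Day 210 telephone contact for all subjects.

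This shows intent but does not remove the conflict. Nothing in the SAP treats a death report as an assessment, Section 5.7 exempts deaths in the double-blind period from the Day 210 status check, and the window sections name the Section 2.5 date as their limit. Two rules for including an event remain. On the strict wording in 2.6.4 the objection mostly stands: the event rule in the same section runs up to EOS, so this is an editorial slip.

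A second reply is that counting deaths after last contact, while survivors without contact stay censored at last contact, pushes event rates upward. That is true. But Sections 2.6.1 and 4.6 already do this in the primary analysis, by counting deaths after withdrawal and censoring event-free withdrawals at the withdrawal date. It is a downside to state, and no reason to leave the text as it is.

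**Conclusion.** The inconsistency is real and limited. Read as written, Section 2.5 excludes from the Post-Randomization and Post-First Dose analyses any VTE-related death that no study assessment follows, against those sections' own account of what they include. For deaths by Day 180, the longer windows can then hold fewer fatal events than the primary one. This assumes that the formula is applied literally and that a death report is not itself an assessment. It changes a subject's status only if no earlier component of the composite had occurred.

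A reader might infer more, and the SAP does not support it:
- **That the main results are affected.** The primary, key secondary, sensitivity and competing-risk analyses all use Up-to-Day 180.
- **That registry deaths are the main loss.** For subjects who withdrew consent or were lost, "the vital status data are obtained through public information (death and other registries) per local guidelines", and Section 4.6 specifies dead or alive. The SAP does not say that registries supply a cause of death, which a VTE-related classification needs.
- **That the number can be estimated.** With 800 randomized, an assumed 10% lost and an assumed 10% to 30% of those dying by Day 210, 800 × 0.10 × (0.10 to 0.30) = 8 to 24 deaths. Those rates are invented and the deaths are from all causes. The VTE-related deaths at issue would be only a part of them, while deaths between visits in the double-blind period are not covered at all.
- **That the summary of deaths in Section 6.2.3 loses cases.** It refers to Day 210/End-of-Study but does not cite the Section 2.5 date.
- **That the loss differs by arm.** Nothing in the SAP shows this.

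**What to change.** In Section 2.5, define EOS as the death date for any subject known to have died on or before Day 210, and otherwise as the last assessment or contact date, including the Day 210 contact. In Section 2.6.4, change the inclusion sentence from events prior to EOS to events on or before EOS. Every death counted in the Up-to-Day 180 window by Day 180 then also falls in the Post-Randomization window, and the text agrees with its own reference to Day 210.

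The cost is one changed date derivation and a few words in 2.6.4, with no new data. The small downside is that deaths after last contact are counted while survivors without contact stay censored at last contact. A sentence in 2.6.3 and 2.6.4 should say so and note that the primary window already accepts the same asymmetry.
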